2.2 Secondary

- 2.21 To determine the best overall response rates (\geq PR) and deep responses (VGPR, CR, sCR) at various stages of treatment: after induction, after SCT, after consolidation and during maintenance.
- 2.22 To determine the overall survival from study entry.

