7.2 Treatment Schedule

	Doses and Schedule				
	Agent	Dose Level	Route	Day	Retreatment
Cycles 1-4 Induction (x 4 cycles)	Ixazomib	4 mg	PO	1, 8, 15	Every 28 days
	Pomalidomide	4 mg	PO	Days 1-21	Every 28 days
	Dexamethasone	40 mg	PO	1, 8, 15, 22	Every 28 days
Cycle 5 Transplantation ^{a,e,f}	Stem cell mobilization ^b followed by single ASCT				
Cycles 6-9 Consolidation ^c (x 4 cycles)	Ixazomib	4 mg	PO	1, 8, 15	Every 28 days
	Pomalidomide	2 mg	PO	Days 1-21	Every 28 days
	Dexamethasone	40 mg	PO	1, 8, 15, 22	Every 28 days
Cycles 10 and Beyond Maintenance (until progression or unacceptable toxicity) ^d	Ixazomib	4 mg	PO	1, 8, 15	Every 28 days

- SCT:** Can be performed per institutional practice. Stem cells collected and cryopreserved ahead of time or collected immediately prior to transplant can be used. Conditioning regimen preference left to the treating physician, but should not be enrolled in any additional therapy trials.
- If not previously collected and cryopreserved.
- If a patient previously has a dose reduction in induction, the consolidation phase will start and continue at reduced dose.
- Ixazomib maintenance would start at 4 mg unless dose has been previously reduced in the Induction or consolidation phase due to a non-hematologic toxicity specifically attributed to Ixazomib.
- Window period is 2-4 weeks between Induction and ASCT; 60-120 days between ASCT and Consolidation and 0-4 weeks between the Consolidation and Maintenance phases.
- Melphalan conditioning followed by stem cell infusion is being considered as 'cycle 5' for logistical reasons only. No additional toxicity data will be collected in the immediate post ASCT period until day 60-100 when the patient returns for routine post ASCT-reevaluation.

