10.6 Required routine reporting

10.61 Baseline and Adverse Events Evaluations

Pretreatment symptoms/conditions to be graded at baseline and adverse events to be graded at each evaluation per CTCAE v4.0 grading **unless** otherwise stated in the table below:

SYSTEM ORGAN CLASS	Adverse event/Symptoms	Baseline	Each evaluation
Investigations	Creatinine increased	X	X
	Neutrophil count decreased	X	X
	Platelet count decreased	X	X
	White blood cell count decreased	X	X
General disorders and administration site conditions	Fatigue	X	X
Gastrointestinal Disorders	Nausea	X	X
	Vomiting	X	X
	# of Stools	X	
	Diarrhea		X
	Constipation		X
Infections and infestations	Sepsis	X	X
Blood and lymphatic system disorders	Febrile neutropenia	X	X
Skin and subcutaneous tissue disorders	Rash maculo-papular	X	X
Nervous system disorders	Peripheral sensory neuropathy	X	X
	Peripheral motor neuropathy	X	X

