13.0 Treatment/Follow-up Decision at Evaluation of Patient

- 13.1 Patients who are MRD negative, sCR, CR, VGPR, PR, or SD (or usCR, uCR, uVGPR, uPR) will continue treatment per protocol.
- 13.2 Patients who develop progressive disease while receiving therapy will go to the event-monitoring phase.
- 13.3 Patients who go off protocol treatment for reasons other than PD will go to the event-monitoring phase per Section 18.0.
- 13.4 Criteria for Discontinuation of Treatment
Patients may discontinue treatment for the following reasons:
- Progressive multiple myeloma
 - Patient refuses further treatment on the trial
 - Patient develops an intercurrent illness that precludes further participation, or requires a prohibited concomitant treatment
 - The Investigator withdraws the patient in the patient's best interests
 - Patient is lost to follow-up (defined as the inability to contact the patient on 3 separate occasions)
 - Administrative reasons (e.g., the patient is transferred to hospice care)
 - An adverse event, which in the opinion of the Investigator, precludes further trial participation
- All attempts should be made to complete the End of Study procedures when the patient discontinues treatment. Patients should go to event monitoring per Section 18.0, unless the patient refuses further study participation or is lost to follow-up.
- 13.5 Criteria for Study Discontinuation
The study may be temporarily or permanently discontinued at any site and at any time. Reasons for study discontinuation may include, but are not limited to, the following:
- Safety concerns

- Poor enrollment
- Non-compliance with the protocol, Good Clinical Practice guidance or other regulatory requirements by the Investigator(s)
- Request to discontinue the trial by a regulatory or health authority or an IRB
- Manufacturing difficulties/concerns

All Investigators and the requisite regulatory authorities will be notified if the study is suspended or terminated for safety reasons. In the case of such termination, the Investigator will notify the IRB.

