16.23 Accrual Rate and Study Duration

We anticipate accruing 2 patients per month to this study, and hence the enrollment period will be approximately 2 years. An individual patient is expected to complete induction, ASCT and consolidation phases within 15 months of enrollment, after which ixazomib maintenance phase will start in which the drug is given until progression or unacceptable toxicity. The minimum duration before results may be reported is expected to be approximately 3.5 years, or until the last patient accrued has been observed for at least 18 months.

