16.32 Secondary Outcome Analyses

- 16.321 The overall response rate will be estimated by the number of patients who achieve a sCR, CR, VGPR, or PR divided by the total number of evaluable patients. All evaluable patients will be used for this analysis. Exact binomial 95% confidence intervals for the true overall response rate will be calculated.
- 16.322 The \geq VGPR response rate will be estimated by the number of patients who achieve a sCR, CR, or VGPR divided by the total number of evaluable patients. All evaluable patients will be used for this analysis. Exact binomial 95% confidence intervals for the true overall \geq VGPR response rate will be calculated.
- 16.323 Overall survival is defined as the time from registration to the last date of documentation of follow-up or death due to any cause. The distribution of overall survival will be estimated using the method of Kaplan-Meier (Kaplan, E. and Meier, P., 1958)
- 16.322 Adverse Events: All eligible patients that have initiated treatment will be considered evaluable for assessing adverse event rate(s). The maximum grade for each type of adverse event will be recorded for each patient, and frequency tables will be reviewed to determine patterns. Additionally, the relationship of the adverse event(s) to the study treatment will be taken into consideration.

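### The adverse event table in 16.32 has no phase or time window, so it cannot separate consolidation or maintenance toxicity from what came before

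*Combined protocol and SAP*

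**What the plan says.** The adverse event paragraph of section 16.32 sets the denominator first: "All eligible patients that have initiated treatment will be considered evaluable for assessing adverse event rate(s". It then sets the statistic: "The maximum grade for each type of adverse event will be recorded for each patient". Frequency tables are to be reviewed for patterns, and relationship to treatment is to be considered. No phase, cycle range, onset time or phase-specific denominator appears there or elsewhere in the document.

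The treatment schedule in 7.2 has four parts: ixazomib, pomalidomide 4 mg and dexamethasone; then ASCT; then the same three drugs with pomalidomide 2 mg; then ixazomib alone. On timing, 16.23 says "An individual patient is expected to complete induction, ASCT and consolidation phases within 15 months of enrollment". Maintenance follows and has no fixed length. Patients can leave before the later parts; for example, 13.2 says "Patients who develop progressive disease while receiving therapy will go to the event-monitoring phase".

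Other outcomes are tied to stage. Secondary goal 2.21 asks for response "at various stages of treatment: after induction, after SCT, after consolidation and during maintenance", and 16.331 lists stages for minimal residual disease.

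On data collection, 10.61 requires "adverse events to be graded at each evaluation per CTCAE v4.0 grading", and the calendar in 4.1 schedules adverse event monitoring before every cycle, including maintenance. The exception is the transplant. A footnote to 7.2 states "No additional toxicity data will be collected in the immediate post ASCT period until day 60-100". Collection resumes only at that re-evaluation visit.

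**The concern.** A maximum grade per event type is a sensible summary when exposure is roughly constant. Here the treatment changes three times, and the last part is open-ended. With no window stated, the natural reading is that the maximum runs over everything collected. Two things follow.

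- **Masking.** Once a patient has had an event type at some grade, a later event of that type at the same or lower grade leaves the table unchanged. This happens even if nobody drops out.
- **Dilution.** Events in maintenance are divided by everyone eligible who started induction, including patients who never received maintenance.

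The rationale gives this some weight. Section 1.2 says the toxicity of existing combinations stands in the way of long-term treatment, and 1.6 presents oral ixazomib as a chance to study convenient maintenance. A reader of the results will want to know how maintenance was tolerated by those who received it, and the planned table does not say.

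**Working it through.** No stated figure is in dispute. For the record, the design in 16.21 and 16.24 (21 evaluable patients, at least 14 successes) reproduces: the exact binomial tail is 0.0946 at a true proportion of 0.50 (stated 0.095) and 0.870 at 0.75 (stated 0.870). Neither figure enters this point.

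**Inputs from the documents**
- Total sample 25, made up of 21 evaluable plus 4 for ineligibility, cancellation, major violation or other reasons (16.22).
- Cancelled patients received no treatment (13.8), and 16.32 counts only eligible patients. The adverse event denominator N could therefore lie anywhere from about 21 to 25, so both are shown.

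**Assumptions, because the documents give no figures**
- m = 15 to 20 patients start maintenance.
- r = 20% of them have a given event in maintenance, so m × r = 3 to 4 patients.
- f = share of those patients who already had that event type at the same or higher grade.

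**Formula:** share of the pooled table that comes from maintenance = m × r × (1 − f) / N. The rate among patients exposed is r = 20%.

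| | N = 25 | N = 21 |
|---|---|---|
| f = 0, m = 15 | 3/25 = 12.0% | 3/21 = 14.3% |
| f = 0, m = 20 | 4/25 = 16.0% | 4/21 = 19.0% |
| f = 0.5, m = 15 | 1.5/25 = 6.0% | 1.5/21 = 7.1% |
| f = 0.25, m = 20 | 3/25 = 12.0% | 3/21 = 14.3% |

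With f = 0 the shortfall is the factor N/m: 25/20 = 1.25 to 25/15 = 1.67 with N = 25, and 21/20 = 1.05 to 21/15 = 1.40 with N = 21. If everyone reaches maintenance the factor is 1 and only masking remains.

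**Masking without dropout.** Section 1.5 describes an earlier phase II study of pomalidomide with dexamethasone in which 21 of 60 patients (35%) had grade 3/4 neutropenia, all first seen in cycles 1 to 3. Borrow 35% as an early rate, assume 20% in maintenance, and assume independence. The ever-rate is 1 − 0.65 × 0.80 = 48%. Maintenance adds 48 − 35 = 13 points instead of 20, and nothing in the table marks those 13 points as arising in maintenance.

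**Precision.** Exact 95% intervals are 2.5 to 31.2% for 3/25, 3.0 to 36.3% for 3/21 and 4.3 to 48.1% for 3/15. Late-phase rates will be imprecise under any tabulation.

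**The case against.** The strongest reply is that 16.32 is silent on phase and does not exclude it. Frequency tables will be reviewed for patterns, and nothing prevents a by-phase version. That is fair as far as it goes: pooling over the whole regimen is inferred from the absence of a window, and the plan does not forbid other tables. But a per-patient maximum grade carries no timing, so reviewing the specified table cannot recover the phase.

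Several further replies stand in full.

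- The size is wholly assumed. With 21 in the denominator and 20 starting maintenance, dilution is one percentage point (19% against 20%), and the intervals overlap almost completely.
- No drug is new in consolidation or maintenance, so the point does not rest on event types that could arise only late.
- Section 2 contains no safety goal, so the table contradicts no objective. The response analyses in 16.321 and 16.322 do not repeat the stages either, which limits the contrast with efficacy.

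A reader might infer that late toxicity would go unrecorded or that safety oversight during the trial is compromised. The documents do not support that. Events are graded at each evaluation, serious events are reported on an expedited basis (10.4), and the investigators, the statistician and the monitoring board review the study at least twice a year (16.41). The stopping rule in 16.42 makes its own count of grade 4 or higher non-hematologic events at least possibly related to treatment. Section 16.25 lets adverse events inform termination but does not name this table.

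A reader might also infer that pooling hides the toxicity of the transplant itself. It does not: immediate post-ASCT toxicity is not collected, so no tabulation could show it.

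**Conclusion.** The point holds as a limitation of the final safety summary. The one table specified cannot separate consolidation or maintenance toxicity from earlier toxicity. Masking follows from the definition of the statistic, given the natural reading that the maximum covers all collected events. Dilution follows if some patients stop before a later phase, which is likely given the exits in section 13 and up to 15 months before maintenance, but which the documents do not quantify.

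Under the assumed 15 to 20 starters and a 20% event rate, maintenance contributes at most 12 to 16% (N = 25) or 14 to 19% (N = 21). That falls to 6 to 12% or 7 to 14% if a quarter to a half of those patients were already counted. These are illustrations, not predictions.

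No decision rule turns on this table, and the primary endpoint, significance level and power are untouched. It is a cheap improvement to reporting, and better settled before the data are seen.

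**What to change.** Keep the overall table and add to 16.32: *The maximum grade of each adverse event type will also be tabulated within induction, consolidation and maintenance, using eligible patients who started that phase as the denominator, with counts shown beside percentages.*

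If a post-ASCT row is shown, label it as covering only events collected from the day 60-100 re-evaluation onward. Without that label the row would make the transplant look safer than the data can show.

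The cost is a few more tables. The three phase tables need no new data, because adverse events are already monitored every cycle. The drawback is small late-phase denominators, which is why counts should accompany percentages. Sample size and significance level do not change.

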16.33 Correlative Analyses

- 16.331 Minimal residual disease will be assessed on bone marrow aspirate in all patients in CR at various stages of treatment: after induction, day # 100 after SCT, after consolidation and during maintenance at one year from initiation of maintenance therapy. The proportion of patients who achieve MRD negative status will be estimated by the number of patients who are MRD negative divided by the total number of evaluable patients who achieve an sCR or CR. Exact binomial 95% confidence intervals for the true MRD negative rate will be calculated.

- 16.324 Engraftment kinetics (WBC and platelet) following single salvage ASCT for relapsed disease will be measured by assessing the timing of recovery of bone marrow function. Neutrophil engraftment will be defined as the first of the three days of neutrophil count above 500/microliter and platelet engraftment as the first day of >20,000 platelets/microliter, untransfused.. The median time to engraftment of neutrophil count and platelet count from the day of infusion of autologous stem cells (day 0) will be summarized using descriptive statistics.

16.4 Data & Safety Monitoring

16.41 Reviews

The principal investigator(s) and the study statistician will review the study at least twice a year to identify accrual, adverse event, and any endpoint problems that might be developing. The Mayo Clinic Cancer Center (MCCC) Data Safety Monitoring Board (DSMB) is responsible for reviewing accrual and safety data for this trial at least twice a year, based on reports provided by the MCCC Statistical Office.

16.42 Adverse Event Stopping Rules

The stopping rules specified below are based on the knowledge available at study development. We note that the Adverse Event Stopping Rule may be adjusted in the event of either (1) the study re-opening to accrual or (2) at any time during the conduct of the trial and in consideration of newly acquired information regarding the adverse event profile of the treatment(s) under investigation. The study team may choose to suspend accrual because of unexpected adverse event profiles that have not crossed the specified rule below.

Accrual will be temporarily suspended to this study if at any time we observe events considered at least possibly related to study treatment (i.e. an adverse event with attribute specified as “possible,” “probable,” or “definite”) that satisfy one of the following:

- if 3 or more patients in the first 10 treated patients experience a grade 4 or higher non-hematologic adverse event at least possibly related to treatment.
- if after the first 10 patients have been treated, 30% of all patients experience a grade 4 or higher non-hematologic adverse event at least possibly related to treatment.

We note that we will review grade 4 and 5 adverse events deemed “unrelated” or “unlikely to be related”, to verify their attribution and to monitor the emergence of a previously unrecognized treatment-related adverse event.

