Toxicology: All studies discussed in this section were conducted with a solution of either MLN2238 or MLN2238 in equilibrium with ixazomib. Because ixazomib was shown to dissociate immediately to MLN2238 upon exposure to plasma in vitro and therefore could not be detected in plasma samples in vitro all doses, concentrations, and PK parameters noted, here and in the IB, are expressed as the boronic acid, MLN2238.

The toxicology studies of MLN2238 were studied in SCID mice bearing human CWR22 tumor xenografts, Sprague-Dawley rats, beagle dogs, and cynomolgus monkeys. Details of these studies are included in the IB.

In Vitro Toxicology: MLN2238 was not mutagenic in a Good Laboratory Practice (GLP)-compliant bacterial reverse mutation assay (Ames assay).

In Vivo Toxicology: Details of the *in vivo* toxicology IV dosing and oral dosing studies are provided in the IB. To summarize, the toxicologic effects seen in the IV and PO studies are qualitatively similar to what was previously observed in rodents dosed with bortezomib. MLN2238 did not cause significant toxicities that have not been previously observed after dosing with bortezomib. Therefore, on the basis of the similarity in the toxicity profile in rats between MLN2238 and bortezomib, MLN2238 is not known to present any additional safety risks beyond those that occur after treatment with bortezomib. In addition, there were no significant findings at tolerated exposures in dogs observed after PO administration that were not seen after IV administration, and similar exposures were tolerated regardless of the route of administration.

The potential risks identified from nonclinical studies in dogs and rats include:

- GI toxicity that could result in nausea, vomiting, diarrhea, dehydration, electrolyte imbalance, bleeding, bowel obstruction (including ileus and intussusception), and sepsis.
- Reduced blood counts manifest as thrombocytopenia, neutropenia, and anemia. Reticulocytopenia was described in animals and may be associated with anemia. Reductions in blood counts may predispose to an increased susceptibility to infection, bleeding, and anemia.
- Peripheral nerve ganglia effects that may be associated with peripheral neuropathy that includes pain, burning sensation, and numbness. Autonomic and motor neuropathy may be observed, as both have been reported for bortezomib.
- Lymphoid cell depletion that may be associated with increased risk of infection, including re-activation of herpes zoster.

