Subject Incidence: A subject counts once for each preferred term. Percentages use the number of treated subjects as the denominator.

Data from ongoing blinded pivotal trials (C16010) are not included.

a Note that rash maculopapular and rash macular represent the two most common terms used to describe rash

The clinical experience with ixazomib also shows early signs of antitumor activity as evidenced by at least a 50% reduction in disease burden in some patients and prolonged disease stabilization in others across all ongoing trials. The antitumor activity has been

seen with single-agent ixazomib, when combined with established therapies, and across the malignancies studied (advanced solid tumors, non-Hodgkin's disease, Hodgkin's disease, relapsed and/or refractory multiple myeloma, relapsed or refractory systemic light chain amyloidosis, and newly diagnosed multiple myeloma) to date.(Kumar et al. 2014, Kumar et al. 2014, Kumar et al. 2014, Richardson et al. 2014)

Though additional data are needed to characterize the clinical benefit of this drug, the emerging data support the ongoing development of ixazomib.

Relapsed and/or Refractory Multiple Myeloma:

Please refer to the ixazomib IB for further information.

- 1.5** ***Pomalidomide:*** Pomalidomide, a thalidomide analogue, is an immunomodulatory agent that displays similar anti-angiogenic activity, but far greater anti-proliferative and immunomodulatory activity compared to the parent drug. Pomalidomide has also been shown to stimulate antibody-dependent cytotoxic T-cell activity (ADCC).

The efficacy of pomalidomide in relapsed myeloma has been shown in multiple trials.(Streetly et al. 2008, Lacy et al. 2009, Lacy et al. 2010, Lacy et al. 2011, San Miguel et al. 2013, Leleu et al. 2015) At tolerated doses (MTD=2 mg QD and 5 mg QOD), pomalidomide has been shown to be active in subjects with relapsed or refractory multiple myeloma (MM) (study CC-4047-00-001). In 45 subjects who received doses of pomalidomide ranging, by cohort, up to 10 mg daily, the most commonly occurring dose-limiting toxicity (DLT) was reversible neutropenia. As with other IMiDs administered to subjects receiving concomitant systemic steroids, deep vein thrombosis (DVT) was seen (in 1 subject each in this study and in its subsequent named patient supply rollover program).

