8.11 Instruction for initiation of a new cycle of therapy

A new cycle of treatment may begin on the scheduled Day 1 of a new cycle if:

- The ANC is $\geq 1.0 \times 10^9/L$ (=1000/microliter)
- The platelet count is $\geq 75 \times 10^9/L$ unless the participant has $\geq 50\%$ bone marrow infiltration in which case a platelet count of $\geq 50 \times 10^9/L$ is allowed
- Any other non-hematologic treatment -related adverse event that may have occurred has resolved to \leq Grade 1 or baseline severity.

If these conditions are not met on Day 1 of a new cycle, the subject will be evaluated weekly and a new cycle of therapy will be held until the toxicity has resolved as described below

If any drug dosing was halted during the previous cycle and was restarted with a one-level dose reduction without requiring an interruption for the remainder of the cycle, then that reduced dose level will be initiated on Day 1 of the new cycle.

If any drug dosing was omitted for the remainder of the previous cycle or if the new cycle is held due to known hematologic toxicity newly encountered on the scheduled Day 1, then the new cycle will be started with a one-level dose reduction. If a new cycle of therapy cannot be restarted within 4 weeks of the scheduled Day 1 due to non-resolution of drug related toxicities, the patient will be removed from protocol therapy and will go to event monitoring.

→ → Use the NCI Common Terminology Criteria for Adverse Events (CTCAE) version 4.0* unless otherwise specified ← ←

8.2 Dose modifications for ixazomib based on adverse events during a cycle (for each cycle during induction and consolidation and maintenance)

CTCAE System/Organ/Class (SOC)	ADVERSE EVENT	AGENT[#]	ACTION^{**}
Blood and lymphatic system disorders	Febrile neutropenia If platelet count $<30 \times 10^9/L$ or ANC $<1.0 \times 10^9/L$ or ANC $>1.0 \times 10^9/L$ (up to LLN) with fever (temperature $>38.5^\circ C$)	Ixazomib	Days 2-15: Ixazomib dose should be omitted. Complete blood count (CBC) with differential should be followed weekly. If ANC is $\geq 1.0 \times 10^9/L$ and/or platelet counts $\geq 30 \times 10^9/L$, ixazomib may be reinitiated with 1 dose level reduction (see Table 8.1). The subsequent cycle will use the reduced dose
Nervous System Disorders	Peripheral motor neuropathy OR Peripheral sensory neuropathy Newly developed Grade 1 with pain or \geq Grade 2	Ixazomib	Reduce dose of ixazomib to the next lower dose level

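### The mandatory accrual-suspension rule in 16.42 does not count treatment-related deaths classed as hematologic

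*Combined protocol and SAP*

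**What the plan says.** Section 16.42 of the combined protocol and SAP contains the only adverse event rule that makes a pause compulsory: "Accrual will be temporarily suspended to this study if at any time we observe events considered at least possibly related to study treatment" and one of two conditions is met. The first is "if 3 or more patients in the first 10 treated patients experience a grade 4 or higher non-hematologic adverse event". The second is "if after the first 10 patients have been treated, 30% of all patients experience a grade 4 or higher non-hematologic adverse event". Both repeat the requirement that the event be at least possibly related to treatment. There is no separate trigger for deaths.

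Two other sentences in 16.42 bear on the point. One is permissive: "The study team may choose to suspend accrual because of unexpected adverse event profiles that have not crossed the specified rule below". The other promises a review of Grade 4 and 5 events judged unrelated or unlikely to be related, "to verify their attribution and to monitor the emergence of a previously unrecognized treatment-related adverse event". That review does not reach events already judged related.

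The protocol does not define non-hematologic. Table 8.2 and section 10.61 place febrile neutropenia under "Blood and lymphatic system disorders". Section 10.61 lists sepsis under infections and infestations. Section 10.32 exempts anemia and falls in blood counts from expedited reporting up to Grade 4 and no further.

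**The concern.** Leaving Grade 4 cytopenias out of the count is a sensible choice, because 10.32 treats them as expected. The same filter also covers Grade 5, and no reason is given for that. A related death then counts or does not count according to the term under which it is recorded. A fatal infection in a neutropenic patient counts if coded as sepsis. On the natural reading it does not count if coded only as febrile neutropenia.

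Marrow toxicity is foreseeable here. In the early pomalidomide study described in section 1.5, "the most commonly occurring dose-limiting toxicity (DLT) was reversible neutropenia". Section 15.27 lists febrile neutropenia and neutropenic sepsis as common with pomalidomide, and section 9.9b names thrombotic thrombocytopenic purpura, which it describes as a blood disorder, as a rare risk with ixazomib. At stake is whether accrual to a 25-patient trial must pause for review when related deaths of this kind occur.

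**Working it through.** **1. The plan's own figures.** The protocol states no operating characteristics for the adverse event rule, so there is none to reproduce. The efficacy rule (at least 14 successes in 21) gives an exact binomial significance level of 0.0946 against 0.095 stated, and power at 0.75 of 0.8701 against 0.870 stated. Both agree, but they do not bear on this point.

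**2. What the rule counts.**

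| Related event | Counted in 16.42? |
|---|---|
| Grade 4 non-hematologic | Yes |
| Grade 5 coded as sepsis | Yes |
| Grade 4 cytopenia | No |
| Grade 5 coded only to a hematologic term | No |

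**3. Worked example.** Among the first 10 patients, suppose two have a related Grade 4 non-hematologic event and two others die of related febrile neutropenia. The count as written is 2, below the trigger of 3. With related deaths included it is 2 + 2 = 4, and accrual pauses. The four must be different people, because the rule counts patients.

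**4. How often the rule fires.** The rates here are assumptions, since the documents give none. Let p be the rate of related non-hematologic Grade 4 or higher events and h the rate of related hematologic deaths, taken as independent. The rule as written sees p; the amended rule sees u = 1 − (1 − p)(1 − h).

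First trigger: P(X ≥ 3), with X binomial on 10 patients. At p = 0.10 this is 1 − (0.3487 + 0.3874 + 0.1937) = 0.0702.

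Both triggers to 25 patients: an exact patient-by-patient recursion. The boundary is 3 up to the tenth patient, then 30% of the number treated, rounded up (4 at 11–13, 5 at 14–16, 6 at 17–20, 7 at 21–23, 8 at 24–25). Each patient's outcome is taken as known before the next is treated.

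With p = 0.10:

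| h | u | First trigger | Both triggers, 25 patients |
|---|---|---|---|
| not counted (as written) | 0.100 | 0.0702 | 0.0799 |
| 0.02 | 0.118 | 0.1045 | 0.1216 |
| 0.05 | 0.145 | 0.1670 | 0.2005 |
| 0.10 | 0.190 | 0.2922 | 0.3638 |

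At p = 0.05 and h = 0.02, the 25-patient probability moves only from 0.0122 to 0.0298. At p = 0.15 it moves from 0.217 to 0.2766 (h = 0.02) or 0.3736 (h = 0.05). The chance of at least one related hematologic death in 25 patients is 1 − 0.98^25 = 0.3965 at 2% and 1 − 0.95^25 = 0.7226 at 5%.

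**5. Enrollment between scheduled reviews.** Section 16.41 requires safety review at least twice a year. At the 2 patients per month in 16.23, 6 × 2 = 12 patients could enter between reviews. If accrual of 25 takes the stated 2 years, the figure is 25 × 6/24, or about 6.

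**The case against.** The strongest reply is that the trial is not blind to these deaths. The team may suspend below the boundary. Section 16.22 makes accrual subject to undue toxicity, 16.25 brings adverse events into any decision to terminate, 16.41 provides regular review by the investigators, the statistician and the DSMB, and 13.5 permits suspension at any time for safety. Section 10.52 requires reporting within 24 hours of any death within 30 days of the last dose, and of later deaths at least possibly attributed to an agent or intervention under the IND. The permissive clause is confined to unexpected profiles, but section 10.2 treats an event of unlisted severity as unexpected, so a fatal cytopenia might qualify. All of this stands. A reader might infer that a hematologic death can never lead to a pause; the documents do not support that. What they lack is any requirement to pause.

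The classification is also open to argument. Sections 10.32 and 10.61 file falls in neutrophils and platelets under investigations, so organ class cannot be the protocol's test of what is hematologic. Treating febrile neutropenia as hematologic is therefore an inference, and a patient who also carries a Grade 4 or higher sepsis code would count. This weakens any claim of certain exclusion but shows that the term needs defining.

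A reader might further infer that marrow-related deaths are among the likeliest treatment deaths, or that myelosuppression is the dose-limiting toxicity of this regimen. Neither is supported. The neutropenia finding comes from a pomalidomide study with doses up to 10 mg daily. The 38% and 35% in section 1.5 are Grade 3 or 4 hematologic toxicity and neutropenia under pomalidomide with dexamethasone, not deaths. The statement that "Reductions in blood counts may predispose to an increased susceptibility to infection, bleeding, and anemia" comes from a list of risks found in dogs and rats, and section 1.3 names gastrointestinal symptoms as the common dose-limiting toxicities of ixazomib. No rate of hematologic death appears anywhere.

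Finally, the amendment is limited: two related hematologic deaths and nothing else in the first 10 patients would still give 2 against a trigger of 3. That is correct. It removes the dependence on coding but does not make a single death a trigger.

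**Conclusion.** The point holds as a gap in the mandatory count. A treatment-related Grade 5 event classed as hematologic adds nothing to either trigger in 16.42, the dividing term is undefined, and every other route to a pause is discretionary or general. The effect on the count is certain from the text; the effect on the chance of suspension is illustrative. With a 10% related non-hematologic Grade 4 or higher rate and independent related hematologic deaths at 2% to 5%, that chance within 25 patients goes from about 8% to between about 12% and 20%. At lower rates the change is small. This is a cheap improvement: it does not affect the efficacy design or its stated error rates.

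**What to change.** In both bullets of 16.42, count patients with *a grade 4 non-hematologic adverse event, or any grade 5 adverse event (hematologic or non-hematologic), at least possibly related to treatment*. Leave the thresholds (3 of the first 10; 30% thereafter) and the exclusion of Grade 4 cytopenias as they are. A line defining non-hematologic, including where febrile neutropenia falls, would settle the remaining coding question at Grade 4.

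The cost is one clause and a somewhat higher chance of a temporary pause, as shown above. No new data item is needed: section 10.62 already collects deaths within 30 days of the last study treatment or procedure and later deaths at least possibly related to treatment. After 30 days, the 24-hour report in 10.52 depends on attribution to an agent or intervention under the IND, so some later deaths may arrive only through the case report forms.
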